13.5.2 Adverse events of special interest

The following AEs of special interest (AESIs) have been defined: SIB, serious infections (i.e. infections meeting the criteria of being an SAE), malignancy diagnosed after randomisation (except basal cell carcinoma, squamous cell carcinoma of the skin, and cervical carcinoma *in situ*), and major adverse cardiac events (MACE) defined as stroke, myocardial infarction, or cardiovascular death. These AESIs have been defined based on the known profile of brodalumab, emerging potential risks in the course of drug development, as well as other risks observed with other immunomodulating biologics used for psoriasis. AESIs must be reported to LEO Pharma as described in [Panel 16](#).

THIS DOCUMENT CONTAINS CONFIDENTIAL INFORMATION AND MUST NOT BE COPIED OR MADE AVAILABLE TO ANY THIRD PARTY WITHOUT THE PRIOR WRITTEN CONSENT OF THE LEO PHARMA GROUP

Panel 16: Adverse events of special interest

AESI	Additional data to be collected
SIB	
Any SIB event must be reported to LEO Pharma Global Safety (Section 13.4.1) on a specific SIB AE form within 24 hours of first knowledge, no matter whether the event is considered serious or non-serious.
 
For SIB events, the specific SIB AE form replaces the standard LEO Pharma SAE form.

Serious infections	
Any serious infection must be reported to LEO Pharma Global Safety (Section 13.4.1) on the standard LEO Pharma SAE form within 24 hours of first knowledge.

MACE	
Any MACE must be reported to LEO Pharma Global Safety (Section 13.4.1) on the standard LEO Pharma SAE form within 24 hours of first knowledge.

Malignancy diagnosed after randomisation (except basal cell carcinoma, squamous cell carcinoma of the skin, and cervical carcinoma in situ)	
Any malignancy events that meet the criteria of being serious must be reported to LEO Pharma Global Safety (Section 13.4.1) on the standard LEO Pharma SAE form within 24 hours of first knowledge. The following should be included, if available:
 
 • Histology report. • Oncology assessment. • Treatment (surgery, radiation, chemotherapy, other). 
If a malignancy event does not meet the criteria of being serious, it should only be reported on the AE form in the eCRF as described in Section 13.3 and reporting within 24 hours is not required.

Abbreviations: AE = adverse event; eCRF = electronic case report form; MACE = major adverse cardiac events; SAE = serious adverse event; SIB = suicidal ideation and behaviour.

13.6 Reporting of other events

13.6.1 Overdose

An overdose is defined as a subject receiving a quantity of IMP which is in excess of that specified in this protocol. An overdose is either accidental or intentional. An accidental overdose must be documented in the eCRF as a medication error as described in Section 13.6.2. An intentional overdose should be documented as misuse or abuse (see Sections 13.6.3 and 13.6.4).

If the overdose is accidental and due to a device deficiency, the device deficiency must be reported as a product complaint as described in Section 9.10.

THIS DOCUMENT CONTAINS CONFIDENTIAL INFORMATION AND MUST NOT BE COPIED OR MADE AVAILABLE TO ANY THIRD PARTY WITHOUT THE PRIOR WRITTEN CONSENT OF THE LEO PHARMA GROUP

LEO Pharma does not recommend specific treatment for an overdose. The investigator will use clinical judgement to treat any overdose if necessary.

13.6.2 Medication error

Medication error refers to any unintentional error in the dispensing or administration of an IMP while in the control of the investigator or subject. Broadly, medication errors fall into 3 categories: wrong medication, wrong dose (including overdose, form, concentration, amount), wrong route of administration.

The medication error category must be documented on the other event form in the eCRF. In addition, AEs originating from a medication error must be recorded on the AE form as separate events. If the AE originating from the medication error qualifies as an SAE, expedited reporting is required (Section [13.4](#)).

If the medication error is due to a device deficiency, the device deficiency must be reported as a product complaint as described in Section [9.10](#).

13.6.3 Misuse

Misuse refers to situations where the IMP is intentionally and inappropriately used not in accordance with the protocol.

The term ‘misuse’ must be recorded on the other event form in the eCRF. In addition, AEs originating from misuse must be recorded on AE form as separate events. If the AE originating from misuse qualifies as an SAE, expedited reporting is required (Section [13.4](#)).

13.6.4 Abuse

Abuse relates to the sporadic or persistent, intentional excessive use of an IMP which is accompanied by harmful physical or psychological effects.

The term ‘abuse’ must be recorded on the other event form in the eCRF. In addition, AEs originating from abuse must be recorded on the AE form as separate events. If the AE originating from abuse qualifies as an SAE, expedited reporting is required (Section [13.4](#)).

13.6.5 Aggravation of condition

Any clinically significant aggravation/exacerbation/worsening of any medical condition(s) (including the trial disease), compared to screening, must be reported as an (S)AE in accordance with Sections [13.3](#) and [13.4](#).

THIS DOCUMENT CONTAINS CONFIDENTIAL INFORMATION AND MUST NOT BE COPIED OR MADE AVAILABLE TO ANY THIRD PARTY WITHOUT THE PRIOR WRITTEN CONSENT OF THE LEO PHARMA GROUP

In case the aggravation/exacerbation/worsening of the trial disease leads to permanent discontinuation of IMP or withdrawal from the trial, ‘lack of efficacy’ should be chosen as the primary reason for discontinuation of IMP / withdrawal from the trial in accordance with Section 10.2.1 and Section 11.6.2.

13.7 Follow-up for final outcome of adverse events

During the trial, the investigator should follow up for final outcome on all AEs (including SAEs). SAEs must be followed up until a final outcome has been established, that is, the follow up may continue beyond the end of the clinical trial. For SAEs which have stabilised and cannot be expected to recover during the trial, for example chronic or stabilised conditions, ‘not recovered’ is accepted as a final outcome. In addition, a statement that the SAE has stabilised or is chronic should be added to the narrative description of the SAE on the SAE form.

13.8 Handling of an urgent safety measure

An urgent safety measure is a measure taken to implement an action/protocol deviation under an emergency. This is defined as “*...the occurrence of any new event relating to the conduct of the trial or the development of the investigational medicinal product where that new event is likely to affect the safety of the subjects, the sponsor and the investigator shall take appropriate urgent safety measures to protect the subjects against any immediate hazard.*” (45).

If the investigator becomes aware of information that requires an immediate change in a clinical trial procedure or a temporary halt of the clinical trial to protect clinical trial subjects from any immediate hazard to their health and safety, the investigator can do so without prior approval from LEO Pharma, regulatory authorities, or IECs.

The investigator must immediately inform LEO Pharma – by contacting the clinical project manager or medical expert – of this change in a clinical trial procedure or of the temporary halt; the investigator will provide full details of the information and the decision-making process leading to the implementation of the urgent safety measure.

LEO Pharma must act immediately upon receipt of the urgent safety measure notification in accordance with internal procedures and local legislation.

THIS DOCUMENT CONTAINS CONFIDENTIAL INFORMATION AND MUST NOT BE COPIED OR MADE AVAILABLE TO ANY THIRD PARTY WITHOUT THE PRIOR WRITTEN CONSENT OF THE LEO PHARMA GROUP

14 Statistical methods

14.1 Sample size

The primary and key secondary endpoints for this trial are having PASI 100 response at Week 16 and the time from randomisation to PASI 100 response. Denoting the Week 16 response rates by π and the sub-distribution hazard rates for having PASI 100 response at time t , measured in weeks, by $\lambda(t)$, the null hypothesis for the primary endpoint,

$$H_0: \pi_{broda} - \pi_{gus} \leq 0,$$

will be tested versus the 1-sided alternative,

$$H_1: \pi_{broda} - \pi_{gus} > 0,$$

while, for the key secondary endpoint, the null hypothesis,

$$H_0: \lambda_{broda}(t) = \lambda_{gus}(t),$$

will be tested versus the alternative,

$$H_1: \lambda_{broda}(t) \neq \lambda_{gus}(t).$$

[Panel 17](#) provides the estimated PASI 100 response rates based on an assessment of the 124 subjects initially randomised to ustekinumab in the AMAGINE-2 and -3 trials, who received brodalumab 210 mg Q2W as rescue therapy starting at Week 16. To qualify for rescue medication in the AMAGINE-2 and -3 trials at Week 16, subjects must have had an sPGA ≥ 3 at Week 16 or an sPGA =2 for at least 4 weeks up to and including Week 16. In order to derive the estimates presented in [Panel 17](#), missing data was imputed using non-responder imputation (NRI).

THIS DOCUMENT CONTAINS CONFIDENTIAL INFORMATION AND MUST NOT BE COPIED OR MADE AVAILABLE TO ANY THIRD PARTY WITHOUT THE PRIOR WRITTEN CONSENT OF THE LEO PHARMA GROUP

Panel 17: PASI response rates after the initiation of brodalumab 210 mg Q2W as rescue therapy among subjects initially randomised to ustekinumab in the AMAGINE-2 and -3 trials

Week	PASI 75 (%)	PASI 90 (%)	PASI 100 (%)	# Imputed by NRI
0	23.4	4.8	0.0	0
2	53.2	19.4	4.8	2
4	67.7	37.1	13.7	3
8	71.0	52.4	29.8	1
12	73.4	58.1	35.5	4
16	78.2	61.3	34.7	9
20	79.0	62.1	42.7	12
24	83.9	62.9	41.1	11
28	79.8	62.9	41.1	14
32	76.6	63.7	38.7	15
36	71.8	57.3	35.5	20

Abbreviations: NRI = non-responder imputation; PASI = the Psoriasis Area and Severity Index; Q2W = every 2 weeks.

[figure not shown]
In order to power this trial, data were simulated from the two-state alternating continuous-time Markov process displayed in [Panel 18](#). The ‘two-state alternating model’ assumes that the transition intensity functions are constant over time. The benefit of the multi-state framework is that it naturally captures the correlation between the time from randomisation to PASI 100 response and the PASI 100 response status at Week 16. Estimates of the transition intensities for brodalumab were obtained by fitting the ‘two-state alternating model’ based on data from the AMAGINE-2 and -3 trials, among subjects receiving brodalumab 210 mg Q2W as rescue therapy after initially being randomised to ustekinumab. The model was fitted using the multi-state model (MSM) package in R, which accounts for the non-informative intermittent inspection process used to obtain the data. For guselkumab, the expected PASI 100 response rates, based on the ‘two-state alternating model’, were derived from the Chapman-Kolmogorov equation,

THIS DOCUMENT CONTAINS CONFIDENTIAL INFORMATION AND MUST NOT BE COPIED OR MADE AVAILABLE TO ANY THIRD PARTY WITHOUT THE PRIOR WRITTEN CONSENT OF THE LEO PHARMA GROUP

$$\pi_{\text{PASI100}}(t) = 1 - \left[\frac{\lambda_{10}}{\lambda_{10} + \lambda_{01}} + \frac{\lambda_{01}}{\lambda_{10} + \lambda_{01}} e^{-(\lambda_{01} + \lambda_{10})t} \right]$$

Panel 18: Two-state alternating model used to simulate patient-level data, in order to power the trial

The estimated transition intensities for the guselkumab arm were then derived by minimising the mean squared error, based on the approximate observed rates extracted from the NAVIGATE trial shown in [Panel 19](#).

THIS DOCUMENT CONTAINS CONFIDENTIAL INFORMATION AND MUST NOT BE COPIED OR MADE AVAILABLE TO ANY THIRD PARTY WITHOUT THE PRIOR WRITTEN CONSENT OF THE LEO PHARMA GROUP

Panel 19: Approximate PASI 100 response rates for the guselkumab arm, reported in the NAVIGATE trial

Week	PASI 100 (%)
0	0.0
4	3.2
8	7.6
12	11.3
16	18.0
20	23.2
24	21.0
28	22.4
36	20.3

Abbreviations: PASI 100 = 100% improvement from baseline in the Psoriasis Area and Severity Index.

Source: (4).

Panel 20 provides the estimated marginal power for the primary and key secondary endpoints and the conjunctive power for rejecting the null hypotheses associated with the primary and key secondary endpoints, while controlling the familywise error rate (FWER) at the 5% significance level (for 2-sided Fisher's Exact and Gray's tests). The power analysis is based on 100,000 simulations, from the alternating two-state model illustrated in Panel 18, assuming the underlying transition intensities for the brodalumab arm were,

- e) $\lambda_{broda,0,1} = 1.00 \cdot \hat{\lambda}_{broda,0,1} = 0.0333$ and $\lambda_{broda,1,0} = 1.00 \cdot \hat{\lambda}_{broda,1,0} = 0.0272$,
- l) $\lambda_{broda,0,1} = 0.98 \cdot \hat{\lambda}_{broda,0,1} = 0.0326$ and $\lambda_{broda,1,0} = 1.02 \cdot \hat{\lambda}_{broda,1,0} = 0.0277$ or
- u) $\lambda_{broda,0,1} = 1.02 \cdot \hat{\lambda}_{broda,0,1} = 0.0340$ and $\lambda_{broda,1,0} = 0.98 \cdot \hat{\lambda}_{broda,1,0} = 0.0266$,

and assuming the underlying transition intensities for the guselkumab arm were

- e') $\lambda_{gus,0,1} = 1.00 \cdot \hat{\lambda}_{gus,0,1} = 0.0158$ and $\lambda_{gus,1,0} = 1.00 \cdot \hat{\lambda}_{gus,1,0} = 0.0435$,
- l') $\lambda_{gus,0,1} = 0.98 \cdot \hat{\lambda}_{gus,0,1} = 0.0155$ and $\lambda_{gus,1,0} = 1.02 \cdot \hat{\lambda}_{gus,1,0} = 0.0444$ or
- u') $\lambda_{gus,0,1} = 1.02 \cdot \hat{\lambda}_{gus,0,1} = 0.0162$ and $\lambda_{gus,1,0} = 0.98 \cdot \hat{\lambda}_{gus,1,0} = 0.0427$.

THIS DOCUMENT CONTAINS CONFIDENTIAL INFORMATION AND MUST NOT BE COPIED OR MADE AVAILABLE TO ANY THIRD PARTY WITHOUT THE PRIOR WRITTEN CONSENT OF THE LEO PHARMA GROUP

The scenarios described in bullet points l), u), l') and u') have been introduced for robustness of the resulting sample size with respect to small perturbations of the transition intensities.

Panel 20: Estimated conjunctive power for rejecting the hypotheses associated with the primary and key secondary endpoints

Sample size per arm	Scenario for transition intensities				Power for the primary endpoint	Power for the key secondary endpoint	Conjunctive power		
	$\lambda_{\text{broda},0,1}$	$\lambda_{\text{broda},1,0}$	$\lambda_{\text{gus},0,1}$	$\lambda_{\text{gus},1,0}$					
N=110	e)	0.0333	0.0272	e')	0.0158	0.0435	83.3%	96.8%	82.5%
N=110	e)	0.0333	0.0272	l')	0.0155	0.0444	85.3%	97.4%	84.6%
N=110	e)	0.0333	0.0272	u')	0.0162	0.0427	80.9%	95.8%	79.9%
N=110	l)	0.0326	0.0277	e')	0.0158	0.0435	80.7%	95.8%	79.7%
N=110	l)	0.0326	0.0277	l')	0.0155	0.0444	82.5%	96.4%	81.6%
N=110	l)	0.0326	0.0277	u')	0.0162	0.0427	78.0%	94.7%	76.8%
N=110	u)	0.0340	0.0266	e')	0.0158	0.0435	85.8%	97.5%	85.1%
N=110	u)	0.0340	0.0266	l')	0.0155	0.0444	87.5%	98.0%	86.9%
N=110	u)	0.0340	0.0266	u')	0.0162	0.0427	83.8%	96.9%	83.0%
N=120	e)	0.0333	0.0272	e')	0.0158	0.0435	87.0%	97.8%	86.4%
N=120	e)	0.0333	0.0272	l')	0.0155	0.0444	88.5%	98.3%	88.0%
N=120	e)	0.0333	0.0272	u')	0.0162	0.0427	84.7%	97.1%	84.0%
N=120	l)	0.0326	0.0277	e')	0.0158	0.0435	84.1%	96.9%	83.3%
N=120	l)	0.0326	0.0277	l')	0.0155	0.0444	86.0%	97.6%	85.3%
N=120	l)	0.0326	0.0277	u')	0.0162	0.0427	81.9%	96.2%	81.0%
N=120	u)	0.0340	0.0266	e')	0.0158	0.0435	89.3%	98.4%	88.8%
N=120	u)	0.0340	0.0266	l')	0.0155	0.0444	90.6%	98.7%	90.2%
N=120	u)	0.0340	0.0266	u')	0.0162	0.0427	87.2%	97.9%	86.6%

Abbreviation: N = number of subjects.

THIS DOCUMENT CONTAINS CONFIDENTIAL INFORMATION AND MUST NOT BE COPIED OR MADE AVAILABLE TO ANY THIRD PARTY WITHOUT THE PRIOR WRITTEN CONSENT OF THE LEO PHARMA GROUP

Based on the above assumptions and results, a sample size of 240 subjects would ensure a conjunctive power of at least 80% in order to reject the null hypotheses for both the primary and key secondary endpoints for all of the illustrated scenarios.

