Anti-drug antibodies (ADA) to brodalumab developed in 2.2% (88/3935) of subjects treated with Kyntheum® for up to 52 weeks in psoriasis clinical trials (0.3% of the subjects had ADA at baseline). Of these subjects, none had neutralising antibodies, and there was no evidence of any association between ADA development and altered pharmacokinetic profile, clinical response, or safety profile. For further details, please see the IB.

Guselkumab

Guselkumab is a fully human immunoglobulin G1 lambda (IgG1λ) monoclonal antibody to the p19 subunit of IL-23 (IL-23p19). It is indicated for the treatment of moderate-to-severe plaque psoriasis in adults who are candidates for systemic therapy. The NAVIGATE trial

THIS DOCUMENT CONTAINS CONFIDENTIAL INFORMATION AND MUST NOT BE COPIED OR MADE AVAILABLE TO ANY THIRD PARTY WITHOUT THE PRIOR WRITTEN CONSENT OF THE LEO PHARMA GROUP

demonstrated that approximately 12% of subjects, who were randomised to guselkumab after inadequate response to ustekinumab, achieved complete clearance (100% improvement in Psoriasis Area and Severity Index score; PASI 100) after 12 weeks, 18% after 16 weeks, 22% after 28 weeks, and 20% after 36 weeks (4).

The most common adverse reactions of guselkumab include upper respiratory tract infections, headache, injection site reactions, arthralgia, diarrhoea, gastroenteritis, fungal skin infections, and herpes simplex infections.

For further details on guselkumab efficacy and safety, please see EU summary of product characteristics (SmPC) for Tremfya® (5).

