5.3 Trial rationale

With increasing availability of novel biologics with new targets, the complexity of choosing the appropriate biologic treatment is ever more challenging for physicians. This applies not only to choosing the most efficacious treatment for the patient, but also to deciding on subsequent treatment options if the patient has inadequate response to a biologic treatment.

Ustekinumab modulates proinflammatory signalling through the inhibition of IL-12 and IL-23. Several trials evaluating efficacy of more modern biologic treatments have demonstrated superiority of the newer agents (targeting IL-17A, IL-23p19, or IL-17RA) over ustekinumab (6-11).

The efficacy of brodalumab for the treatment of psoriasis has been confirmed in 3 placebo-controlled phase 3 trials, 2 of which included an ustekinumab comparator arm (AMAGINE-2 and -3). A subanalysis of these trials showed that rescue treatment with brodalumab improved skin outcomes among subjects with inadequate response to ustekinumab (9, 10, 12).

The head-to-head trial of guselkumab versus ustekinumab in subjects inadequately treated with ustekinumab (NAVIGATE trial) has demonstrated increased psoriasis improvement in subjects randomised to guselkumab compared with those randomised to continue on ustekinumab (4).

By comparing data from the AMAGINE and the NAVIGATE trials, it was concluded that brodalumab treatment would lead to significantly higher PASI 100 rates than guselkumab treatment after 16 weeks of treatment (34.7% vs. approximately 18%, respectively) (4, 12). No trials have, however, directly compared IL-17RA antagonism with IL-23p19 inhibition.

THIS DOCUMENT CONTAINS CONFIDENTIAL INFORMATION AND MUST NOT BE COPIED OR MADE AVAILABLE TO ANY THIRD PARTY WITHOUT THE PRIOR WRITTEN CONSENT OF THE LEO PHARMA GROUP

Therefore, the primary objective of this trial is to compare the efficacy of brodalumab versus guselkumab in adult subjects with moderate-to-severe plaque psoriasis and inadequate response to ustekinumab, thereby providing results that could support decision-making in the clinical setting.

The primary endpoint is PASI 100 at Week 16. PASI 100 is chosen due to substantial evidence highlighting the importance of complete clearance from the patient's perspective, improving quality of life and decreasing the disease burden (13). Moreover, PASI 100 allows better and most accurate differentiation between highly efficacious treatments available for the treatment of psoriasis today.

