5.4.1.1 Main analysis

For each of the 250 complete datasets, the treatment effect will be estimated, along with the associated standard error, from a logistic regression model, adjusted for baseline body weight (≤ 100 kg, > 100 kg) and the baseline value of the underlying response variable. Based on Rubin’s rules, a combined estimate and standard error for the treatment effect will be calculated and the associated t statistic will be used for testing the null hypothesis that the response rate for the brodalumab arm is less than or equal to the rate for the guselkumab arm, against the alternative that brodalumab is superior to guselkumab. The statistical test will be based on the odds ratio or, equivalently, on the log-odds ratio as expressed through the treatment coefficient in the logistic regression model. In practice, the t test will be carried out as a two-sided test at the 5% significance level, where the null hypothesis will only be rejected in favour of the stated alternative if the treatment effect estimate is in favour of brodalumab. This corresponds to a one-sided test at the 2.5% significance level.

To quantify the magnitude of the potential treatment effect, estimates of the LS-mean risk difference and odds ratio will be presented along with the associated 95% confidence intervals

THIS DOCUMENT CONTAINS CONFIDENTIAL INFORMATION AND MUST NOT BE COPIED OR MADE AVAILABLE TO ANY THIRD PARTY WITHOUT THE PRIOR WRITTEN CONSENT OF THE LEO PHARMA GROUP

(CIs), based on combining estimates and associated standard errors from the 250 analyses using Rubin's rules.

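### Does the sample-size calculation overstate power because its model puts guselkumab's Week 16 PASI 100 rate below the reported 18.0%?

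*Protocol*

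**What the plan says.** Protocol Section 14.1 simulates both endpoints from a two-state model that "assumes that the transition intensity functions are constant over time". The guselkumab intensities were "derived by minimising the mean squared error, based on the approximate observed rates extracted from the NAVIGATE trial" and tabulated in Panel 19, where the Week 16 value is 18.0%. Section 5.2 gives the same series in the text: "18% after 16 weeks, 22% after 28 weeks, and 20% after 36 weeks". Section 5.3 sets about 18% for guselkumab against 34.7% for brodalumab at Week 16.

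Panel 20 crosses three brodalumab scenarios (e, l, u) with three guselkumab scenarios (e', l', u'). The l and u variants move each intensity by 2% and "have been introduced for robustness of the resulting sample size with respect to small perturbations of the transition intensities". Power is given "for 2-sided Fisher's Exact and Gray's tests". At 120 per arm the base case e/e' has 87.0% primary and 86.4% conjunctive power. The lowest row, l/u', has 81.9% and 81.0%. The section concludes that, with 240 subjects, conjunctive power is "at least 80% in order to reject the null hypotheses for both the primary and key secondary endpoints for all of the illustrated scenarios".

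The confirmatory test is not Fisher's. SAP Section 5.4.1.1 bases it "on the log-odds ratio as expressed through the treatment coefficient in the logistic regression model".

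**The concern.** The primary endpoint is read at one visit, Week 16, and the fitted guselkumab curve is low at that visit. No row of Panel 20 uses the comparator rate that the protocol itself cites, and perturbations of 2% are too small to reach it. A comparator rate set too low inflates the assumed difference and therefore the power.

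Amendment 3 cut the trial from 260 to 240 subjects on the strength of this calculation. If the true margin over 80% were negative, the reduction would rest on an optimistic input that readers cannot see, because the implied Week 16 rates are not printed.

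**Working it through.** **Inputs.** The formula and intensities are in Protocol 14.1. The reported rates are in Panel 17 (brodalumab 34.7%, 124 subjects, 9 imputed as non-responders at Week 16) and Panel 19 (guselkumab 18.0%). There are 120 subjects per arm and the tests are two-sided at 5%.

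**Implied Week 16 rates.** With a = λ01 and b = λ10, π(16) = a/(a+b) × (1 − exp(−16(a+b))).

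- Brodalumab e: 0.0333/0.0605 × (1 − exp(−0.968)) = 34.1%. Likewise l gives 33.5% and u gives 34.8%.
- Guselkumab e': 0.0158/0.0593 × (1 − exp(−0.9488)) = 16.3%. Likewise l' gives 16.0% and u' gives 16.8%.

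**Source of the gap.** A least-squares refit to Panel 19 returns 0.01583 and 0.04352, the protocol's values to rounding, so this is not a transcription error. Fitted minus reported, in points:

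| Week | 4 | 8 | 12 | 16 | 20 | 24 | 28 | 36 |
|---|---|---|---|---|---|---|---|---|
| Difference | +2.4 | +2.5 | +2.3 | −1.7 | −4.7 | −0.8 | −0.8 | +3.2 |

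Reaching 18.0% takes an 8.5% shift of both intensities (λ01 up, λ10 down).

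**Panel 20 reproduced.** Primary power comes from exact enumeration of Fisher's test over two binomials. All 18 stated values agree within 0.3 points. Conjunctive power comes from 40,000 simulated trials at the protocol visits, with Fisher's test plus a log-rank test (equal to Gray's test when there are no competing events).

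| Case, 120 per arm | Difference (points) | Primary, Fisher | Primary stated | Primary, logistic Wald | Conjunctive, Fisher | Conjunctive stated |
|---|---|---|---|---|---|---|
| e/e' | 17.8 | 86.9% | 87.0% | 89.3% | 86.6% | 86.4% |
| l/u' | 16.7 | 81.9% | 81.9% | 85.0% | 80.9% | 81.0% |
| 34.7% vs 18.0% | 16.7 | 80.8% | no row | 84.0% | 79.4% to 80.5% | no row |

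The range in the last row covers repeated runs and different ways of moving the intensities to reach 18.0%. With the logistic test the corresponding conjunctive range is 82.5% to 83.7%.

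**Precision of the inputs.** The 95% half-width for 34.7% of 124 is 1.96 × √(0.347 × 0.653/124) = 8.4 points. The size of the guselkumab arm in the source trial is not in the documents. Assuming 100 to 200 subjects, the half-width at 18% is 7.5 to 5.3 points. The 1.7-point gap is small beside either.

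**A pull in the other direction.** The 34.7% is 43/124, with 9 missing subjects counted as non-responders. The planned analysis imputes missing scores under missing at random for subjects still on treatment. The upper bound is 43/115 = 37.4%, and 37.4% vs 18.0% gives 90.5% Fisher power. The applicable value lies between 80.8% and 90.5%, since discontinuations still count as non-response.

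**The case for a change.** The strongest case for a change is that the misfit is systematic. The curve is high early, low at Weeks 16 and 20, and the shortfall falls on the one visit and the one arm where it flatters power. Brodalumab is off by only 0.6 points (34.1% against 34.7%). A robustness check that never reaches a reported input is a weak one. Row l/u' matches the 16.7-point difference only by lowering brodalumab, and its 81.9% is still above 80.8%. At the reported rates, 130 per arm would have given 84.0% with Fisher's test, so the cut to 120 used up most of the margin. Holding brodalumab at the protocol's e, l and u rates and moving only guselkumab to 18.0% gives Fisher primary power of 78.1%, 74.7% and 81.4%. SAP Section 3 still points to this calculation although SAP Section 6 says the trial ended early.

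The description of the misfit stands, and so does the smaller margin. The rest carries less weight. Row l/u' differs from the reported-rate case by only 1.1 points of primary power (81.9 − 80.8). The 78.1% and 74.7% figures pair an observed guselkumab rate with modelled brodalumab rates below the observed one, so they are not power at the reported rates. Fitting all visits is disclosed, and it lets one model carry the correlation between Week 16 status and time to response. Preferring a single visit's value, which Panel 19 itself labels approximate, is partly judgement. Reporting the number randomised after the early end is a separate matter from the Panel 19 fit.

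**Conclusion.** No change is needed. The fitted model understates the reported guselkumab Week 16 rate by 1.7 points, which makes base-case primary power about 6 points higher than at the reported rates (87.0% against 80.8%, Fisher). Panel 20 is nonetheless computed correctly, and its conclusion is confined to the scenarios shown and holds for them. At the reported rates, conjunctive power is about 80% with Fisher's test and about 83% with the unadjusted logistic test, so 120 per arm remains defensible.

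Printing the implied rates or adding a row would show figures that a reader can already derive from the printed formula and intensities. It would alter no sample size, analysis or conclusion, and recruitment can no longer respond because the trial was ended ahead of schedule.

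This rests on three assumptions: complete Week 16 data, no competing discontinuations in the simulation, and an unadjusted logistic test standing in for the covariate-adjusted one.
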